16.3.8 Aim 3 Adequacy of sample size

The statistical approaches that will be used in the ultimate analysis will be specified *a priori* in a Statistical Analysis Plan. Here, we provide an assessment of the adequacy of the sample size based on reasonable assumptions, recognizing that the final methods will be highly optimized using rapidly developing methodology.

Among the estimated 1500 ventilated patients with HME fluid collected, we estimate that 1050 will have sepsis (both pulmonary and non-pulmonary), 600 will have ARDS, and 600 will have pneumonia. All subgroups are larger than $n=500$, which is sufficient for the proposed analyses as shown in the rationale for the cohort sample size, and is true even if feature quality is suboptimal.⁸ For example, Hsieh et al,⁹ showed that with $n=600$ (the smallest subgroup) a multivariable logistic regression to detect an association between a covariate of interest (COI) and the response variable, has 90% power to detect an odds ratio of 1.55 to 1.60, for each standardized unit increment in the COI when the COI is moderately correlated with other covariates in the model (multiple correlation of 0.2 to 0.5).

For analysis of long-term respiratory outcomes, approximately 500 hospital survivors will have follow-up testing (PFT, CT) collected and among these we anticipate that the majority will have been mechanically ventilated during the acute hospitalization. Enrollment of mechanically ventilated patients in the in person LTO cohort will be monitored over time and sampling strategy can be adjusted to further enrich for mechanically ventilated patients if needed. Assuming just 200 mechanically ventilated patients, the sample size is sufficient for complex regression models with interactions and regression splines; Cohen's F^2 will be 0.08 for 90% power and 5% type I error rate when the base model has 10 degrees of freedom and the new model adds 4 degrees of freedom (e.g., adding a three-level categorical variable and its interaction with two-level categorical variable). Thus, power is sufficient to detect a medium effect in terms of improvement in model fit by including new respiratory phenotypes and their interactions, represented by relative increase in R^2 values.

Finally, of the 1500 subjects that we expect will be on mechanical ventilation in the study, we anticipate that 700 will have NBBAL. We can assess the association between NBBAL and blood expression of 500 candidate genes and up to 50 WGCNA networks. We estimate an FDR adjusted significance threshold of 0.0047 assuming 10% of genes are truly associated in blood and BAL, 80% power and a 5% FDR. Using this adjusted significance threshold, 700 participants will provide 80% power to detect correlations of 0.14 between blood and NBBAL expression measures.

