7.2 Anticipated Study Population

7.2.1 Enrollment targets

The APS Consortium investigators recognize that phenotyping efforts require adequate numbers of patients within specific groups for which phenotyping is desired. Additionally, care will be taken to promote representation among multiple sociodemographic groups. The APS Consortium recognizes three key priorities for representation: (1) sociodemographic representation, (2) distribution across the historical syndromes of ARDS, pneumonia, and sepsis, and (3) patients in whom deep respiratory samples are available (patients ventilated through an endotracheal tube).

The APS Consortium Steering Committee will regularly monitor participant characteristics of the overall cohort and the subset with in-person long-term outcome visits to promote adequate representation of several groups. The Steering Committee will work to achieve the following goals:

- i. Adequate race, ethnicity, and sex representation, including inclusion of participants reporting Black race or Hispanic ethnicity at or above percentages reported for these groups in US census data;
- ii. Adequate representation from rural areas, based on urban-rural classifications by the US Census Bureau following the 2020 census. A rural area is defined as any area in the US outside the 2,646 recognized urban areas. An urban area is defined as a census area with >2,000 housing units

or >5,000 population. A list of urban areas is available upon request. US Census Bureau definitions of urban and rural are available at: <https://www.census.gov/programs-surveys/geography/guidance/geo-areas/urban-rural.html>;

- iii. Adequate representation from the historical ARDS, pneumonia, and sepsis categories, with at least 1000 patients with ARDS, 2000 patients with sepsis, and 2000 patients with pneumonia in the overall cohort, recognizing that a given patient may count toward multiple categories;
- iv. Adequate numbers of patients who received invasive mechanical ventilation in the overall cohort (target: ≥ 1000 patients) and long-term outcome subset (target: ≥ 150 patients).

The APS Steering Committee will review participant characteristics of the enrolled cohort overall and by site no less frequently than every 3 months (quarterly) during the enrollment period. This review will include data tables that display participant characteristics for the following categories:

- Sociodemographics, including race, ethnicity, and sex

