9.2.4 Post-hospital in-person visits

Expanded biospecimen, imaging, and data collection will be completed for a subset of enrolled participants. Post-hospital in-person visits may occur in a variety of settings, including but not limited to a hospital, clinic, or the participant's home. Participants who live within a reasonable drive time (to be determined by the local site) of a follow-up visit location and are fluent in either English or Spanish will be eligible to participate in in-person follow-up visits. Participating in the in-person long-term outcome visits is limited to patients fluent in English or Spanish because information gathered during these visits will be paired with survey data and the participating sites have capacity to administer the surveys only in English or Spanish. Enrollment for in-person follow-up will close after approximately 600 patients have completed a 3-month in-person follow-up visit.

The first 600 participants to complete a 3-month in-person study visit will constitute the in-person long-term outcome cohort. The 600-participant in-person long-term outcome cohort will be filled on a “first come” basis with eligible, consenting participants.

Eligibility for the in-person long-term outcome cohort:

1. Enrolled in the APS Consortium Study during the index hospitalization (all participants in the in-person long-term outcome cohort must also be in the primary APS study cohort).
2. Survived to hospital discharge
3. Fluent in English or Spanish
4. Live within a reasonable distance of the in-person follow-up visit location to enable completion of 3 in-person visits without undue burden on the participant or study personnel (the threshold distance will be defined at each site based on local context)
5. Consent for the primary APS Study, including the long-term outcome surveys (informed consent document #1)
6. Consent for the in-person long-term outcome follow-up visits (informed consent document #2)

Study Procedures at in-person long-term outcome follow-up visits:

In-person follow-up will include the following assessments at 3, 6, and 12 months:

1. Short physical performance battery (SPPB), which includes balance test, timed 4-meter walk test, and chair stand test
2. Handgrip strength (dominant hand only; unless that hand is impaired)
3. CNS-Vital Sign (computerized test that assesses cognitive function)

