Study-specified Chest CT scan at 12-month visit (Not completed on pregnant participants)	Upload up to 1 scan per participant. Scheduled study-protocol thin-cut chest CT scan. Funded by study budget. If a similar scan has been completed clinically in the prior 6 weeks before 12-month visit, upload the clinical scan and do not repeat as a research procedure.	1 per participant among those who complete the 12-month follow-up visit [number of scans = 500]
Study-specified pulmonary function tests (spirometry and DLCO) at 12-month visit	Record results of up to 1 pulmonary function test battery per participant. Scheduled study specified spirometry and DLCO. Funded by study budget. If similar pulmonary function tests have been completed clinically in the prior 6 weeks before 12-month visit, record the results of those tests and do repeat as a research procedure.	1 per participant among those who complete the 12-month follow-up visit [number of PFT batteries = 500]

11. Use of Data and Biospecimens

Data, biospecimens, and radiographic images collected in the APS Consortium will be used for 3 purposes:

1. Completion of APS Consortium-wide science as outlined in appendices to this protocol (funded by the APS Consortium budget).
2. Completion of APS Clinical Center-specific science as outlined in grants proposals from Clinical Centers investigators and selected for funding via the NIH peer review process (funded by the APS Consortium budget).
3. Banking for use in future ancillary studies conducted by investigators both inside and outside the APS Consortium (biobanking is funded by the APS Consortium budget but ancillary studies for use of bio-banked data and specimens is not funded by the APS Consortium budget).

During conduct of the APS Consortium study procedures outlined in this master protocol, data, biospecimens, and radiographic images will be collected by enrolling sites and transmitted to the APS Consortium Coordinating Center at Vanderbilt University Medical Center. Data and biospecimens will be organized and catalogued at the coordinating center. The coordinating center will distribute data and biospecimens as needed to complete Consortium-wide science and Clinical Center-specific science. Additionally, the coordinating center will periodically transmit data and biospecimens to repositories managed by the National Heart, Lung, and Blood Institute (NHLBI) -- BioData Catalyst (data repository) and BioLINCC (biospecimen repository).

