For long-term outcomes, we will focus first on two key hypotheses. First, we hypothesize that acute lung epithelial injury as measured by HME fluid RAGE and SP-D will be associated with development of fibrotic lung changes (increased lung fibrosis scoring on CT, decreased FVC). Second, we hypothesize that the severity of lung endothelial injury as measured by HME fluid Ang-2 and ICAM-1 will be associated with long-term destruction of the lung vascular bed as measured by DLCO. The dependent variables of interest are continuous variables and will be DLCO, FVC, lung fibrosis score. Independent variables include age, sex, HME biomarker data from both day 1 and latest day available, ventilator settings, RALE score, duration of mechanical ventilation, underlying cause of ARF (pneumonia, ARDS, sepsis, other). The initial proposal is for use of linear regression models; dependent variables may be log-transformed to improve fit. Analyses done are expected to include the entire cohort, as well as in subgroups divided by clinical syndrome (pneumonia, ARDS, sepsis). To determine whether long term respiratory outcomes differ by any *de novo* respiratory phenotypes, we can include the phenotype variable and its interaction terms with the main independent variables of interest.

We plan to check for concordance and discordance between novel respiratory phenotypes identified in this Aim and previously derived phenotypes based on clinical and biomarker data and the LCA approach. We will then assess reasons for concordance and discordance. If the same number of clusters are identified with each analysis, standard metrics including Cohen's Kappa will be used to assess the degree of concordance. Identifying a different number of clusters for systemic vs. respiratory phenotypes, or the same number with lack of concordance, may indicate that respiratory phenotypes differ from systemic inflammatory phenotypes. When different numbers of clusters are identified between aims, correlation between cluster variables will be assessed, as well as evaluating whether some clusters function as sub-clusters of those identified in other aims.

Finally, a key question is whether the biologic mechanisms that form the basis for NBBAL endotypes are reflected in the blood. This can be achieved by exploring targeted gene expression profiles and weighted gene cluster network analysis (WGCNA) in bulk RNA seq between peripheral blood PBMCs and NBBAL.

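### Aim 3's 12-month lung-function power rests on 200 ventilated patients, a number that the protocol's own target and ventilated counts do not secure

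*Protocol*

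**What the plan says.** **Power statement (16.3.8).** For long-term respiratory outcomes the protocol writes: "Assuming just 200 mechanically ventilated patients, the sample size is sufficient for complex regression models with interactions and regression splines". The supporting figure is a detectable Cohen's f² of 0.08 (power 90%, alpha 0.05) for a test that adds 4 parameters to a base model using 10. From this the section concludes that "power is sufficient to detect a medium effect in terms of improvement in model fit". The same paragraph expects most of the approximately 500 survivors with PFT and CT to have been ventilated during the acute hospitalization. It also says that ventilated enrolment in the in-person cohort will be monitored and that sampling can be shifted towards these patients if necessary.

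**Target (7.2.1, item iv).** The Steering Committee is to work towards "Adequate numbers of patients who received invasive mechanical ventilation in the overall cohort" (at least 1000) and in the long-term outcome subset (at least 150).

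**How the subset forms (9.2.4).** "The first 600 participants to complete a 3-month in-person study visit" make up the in-person cohort, filled first come among eligible, consenting participants. The section reserves no places by ventilation status.

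**When lung function is measured (9.2.4, Table 10).** Spirometry, DLCO and the study CT are done at 12 months only, with "number of PFT batteries = 500".

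**Ventilated share of the whole cohort.** Table 9 has 1333 of 4000 on invasive ventilation at Day 0. Section 16.3.3 estimates 1500 of 4000 ventilated in the first four study days.

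**The concern.** The wording presents 200 as a cautious figure, well below what is expected. Yet the number that is monitored is 150, it is counted in a group of 600 at month 3, and the outcomes exist only for the 500 or so tested at month 12. The Steering Committee could see its in-person target met while the 12-month lung-function analysis has far fewer than 200 ventilated patients. The expected majority is also higher than either ventilated share that the protocol gives.

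At stake is whether the 90% power for f² = 0.08 can be relied on. Timing matters: the subset closes once about 600 people have completed the 3-month visit, so a statistical analysis plan written later cannot bring in ventilated participants who were not recruited.

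**Working it through.** **Inputs from the protocol**
- N = 200 ventilated, base model 10 df, 4 added df, alpha 0.05, f² = 0.08, power 90% (16.3.8)
- In-person subset about 600 at month 3 (9.2.4)
- About 500 with 12-month tests (Table 10, 16.3.8)
- Ventilated target in the subset at least 150 (7.2.1)
- Ventilated in the cohort: 1333/4000 = 33.3% (Table 9, Day 0) and 1500/4000 = 37.5% (16.3.3)

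**Method.** F test for the increment in R²: numerator df u = 4, denominator df v = N − 10 − 4 − 1 = N − 15, noncentrality λ = f² × N.

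**Step 1: reproduce the plan's figure.** At N = 200, v = 185. For f² = 0.08, λ = 0.08 × 200 = 16, and power is 90.4%. The f² giving exactly 90% power is 0.079. With Cohen's alternative λ = f² × (u + v + 1) = f² × 190, the values are 88.7% and 0.083. Both versions round to f² = 0.08, so the stated figure is right.

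**Step 2: what the protocol's counts imply at month 12.**
- Target carried forward: 150 × 500/600 = 125. This assumes that ventilated patients are retained at the overall rate.
- Share at Day 0: 500 × 1333/4000 = 167.
- Share in the first four study days: 500 × 1500/4000 = 187.5, about 188.
- A majority of 500 would be more than 250.

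The Day 0 share applied to the 600 at month 3 gives 600 × 1333/4000 = 200. The protocol does not say where its 200 comes from, but lung function is measured in the 500, not the 600.

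**Step 3: power at those numbers (λ = f² × N).**

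| N ventilated and tested | v | Power at f² = 0.08 | f² at 90% power | Power at f² = 0.15 |
|---|---|---|---|---|
| 200 | 185 | 90% | 0.079 | >99% |
| 188 | 173 | 88% | 0.084 | 99% |
| 167 | 152 | 84% | 0.095 | 99% |
| 150 (target met, no loss) | 135 | 79% | 0.106 | 98% |
| 125 (target met, 500/600 retained) | 110 | 69% | 0.129 | 94% |

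With Cohen's λ the N = 125 row becomes 65%, 0.140 and 92%. Reaching 90% power needs N = 198 for f² = 0.08 and N = 109 for f² = 0.15. The value 0.15 for a medium effect is an assumption, because the protocol attaches no number to the word.

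**Step 4: month-3 target that matches the assumption.** 200 × 600/500 = 240.

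**The case against.** **The 150 is a minimum, not a forecast.** This stands. The protocol nowhere predicts 125. That number requires recruitment to stop at the minimum and ventilated patients to be retained at 500/600.

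**Monitoring and enrichment are provided for.** This stands in part. Section 16.3.8 promises both, and 7.2.1 adds quarterly review with an action plan. It would be wrong to say that the plan has no safeguard. But the only threshold written down is 150 at subset level, below the 200 tested on which the power depends, and 9.2.4 still describes first-come filling. The sections need reconciling.

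**The 167 to 188 range may be low.** This stands. The underlying counts cover Day 0 and the first four study days, while the majority statement refers to the whole acute hospitalization. At 188 the loss is trivial, 88% against 90%.

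**The medium-effect conclusion survives.** This stands if medium means f² = 0.15: power is 94% at N = 125 (92% with Cohen's λ).

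**A stronger reading about covariates.** Section 16.3.7 says "Independent variables include age, sex, HME biomarker data from both day 1 and latest day available, ventilator settings, RALE score, duration of mechanical ventilation", and smoking, prior lung disease and height are not named. A reader might infer that the model wrongly adjusts for a mediator and omits key confounders. The document does not support calling this an error. The list is open-ended, the linear model is an initial proposal within one potential approach, and the final model is left to a filed analysis plan. The hypotheses are stated as associations. The biomarkers also include the latest available day, and HME fluid is collected only during ventilation, so for that predictor duration is not simply downstream.

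**Conclusion.** The point holds as a mismatch between a power assumption and the target meant to protect it, not as a calculation error. The f² of 0.08 at N = 200 is correct. The protocol's own figures do not secure 200 ventilated patients with 12-month tests. They give about 125 if the target is only just met (assuming equal retention), and about 167 to 188 at the cohort's stated ventilated share, which may be low for the whole stay. Power for f² = 0.08 then lies between about 69% and 88% instead of 90%, and the detectable f² at 90% power between about 0.13 and 0.084. The majority expectation has no support in the protocol's counts.

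A reader might infer that the study will deliver only 125, or that Aim 3's long-term analysis is underpowered outright. Neither follows: 125 is a floor scenario, enrichment is allowed, and a medium effect of f² = 0.15 (assumed) remains detectable with about 94% power at that number. The covariate question is no part of this conclusion.

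**What to change.** Choose one of two.

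1. **Restate the power.** In 16.3.8, give the detectable f² at 90% power over N = 125 to 200 (about 0.13 down to 0.08), say what value is meant by a medium effect, and either support the majority expectation with a count or delete it. This costs only wording.
2. **Protect the assumption.** In 7.2.1 item iv, raise the in-person ventilated target from 150 to about 240 at month 3 (240 × 500/600 = 200), so that the monitoring threshold matches the power statement. Amend 9.2.4 so that first-come filling is consistent with the enrichment promised in 16.3.8. No extra enrolment is needed, but there will be fewer non-ventilated participants among the 600. This has to be decided before the subset fills.

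As an optional suggestion for the analysis plan, report the day-1 biomarker models both with and without duration of ventilation.

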16.3.9 Aim 3 Expected Output

We anticipate that we will find lung-specific phenotypes, and that sepsis, ARDS and pneumonia will share respiratory phenotypes that will differ from systemic hyper- and hypo-inflammatory phenotypes. In addition, we expect to definitively answer the longstanding question as to how well the biological processes in the airspace can be reflected in the plasma. This study will allow direct comparison between plasma and airspace biomarkers from contemporaneous samples in a large and clinically diverse cohort allowing us to directly address that question.

With regard to long-term outcomes, we anticipate that we will identify key biological signatures in the airspace that will correlate with different long-term outcomes. Specifically, lung epithelial injury biomarkers will correlate with long term restrictive/fibrotic lung dysfunction, and lung endothelial injury markers will correlate with reduced DLCO. It may be that our selected biomarkers do not correlate with these outcomes, in which case we will explore associations with biomarkers of other mechanistic pathways that will be measured for the respiratory LCA.

Lastly, we expect that results from this analysis will shed light on relationships between the alveolar environment and systemic disease. As an example, it has been suggested that COVID-19 pneumonia is driven by self-sustaining inflammatory circuits. However, it is unclear how this mechanism contributes to systemic inflammation and extra-pulmonary organ dysfunction. Similarly, it is unclear how severe pulmonary infections set the stage for impaired systemic immune function. Head-to-head assessment of gene expression pathways and network modules between lung and blood will help address these questions and will define central biologic mechanisms that contribute to disease pathogenesis in the lung versus the periphery.

16.4 Appendix D (Aim 4): Determine trajectories of established phenotypes over time, and utilize longitudinal data to identify novel phenotypes of APS during the acute phase and during recovery.

16.4.1 Aim 4 Background and Rationale

Molecularly-defined phenotypes with different predicted survival and differential response to multiple randomized therapies have been validated in multiple critical illness populations with APS.^{1,2,3} However, the vast majority of existing work has been performed using plasma protein and clinical phenotyping from only the earliest timepoint, and not considering the dynamic nature of class-defining markers over time. We hypothesize that the trajectory of molecular phenotypes have important prognostic information about patients' condition, and that the resolution of 'hyperinflammatory' phenotype will associate with improved survival. Furthermore, by considering new plasma proteomic features, transcriptomic features, and microbial data over time, we hypothesize that novel phenotypes with distinct biological dysregulation can be identified, which in turn may yield novel precision treatment paradigms for APS.

